8.1.4. Acute cardiac events

Acute cardiac events will be recorded based on the clinical evaluation.

Acute CV events are defined as an inpatient or emergency department visit with a primary diagnosis of any of the following conditions (International Classification of Diseases, 9th Revision, Clinical Modification (ICD-9-CM) codes are also shown). Coronary heart disease (ICD-9-CM codes 410-414), cardiac arrhythmia (ICD-9-CM code 427), heart failure (ICD-9-CM code 428), or ischemic stroke (ICD-9-CM codes 433-434) (Wang et al 2018).

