8.3.4. Recording of AEs and SAEs

During the study, site personnel will evaluate and record any change in the pre-existing condition(s) and/or the occurrence of any AEs.

Subjects will be questioned for the occurrence of any new or worsening sign or symptom at each study visit. The Investigator or designee will enquire about AEs by asking non-leading questions, such as in the following examples:

At the first scheduled AE enquiry on Day 0 (pre-dose) subjects will be asked:

“How are you feeling?”

At subsequent scheduled intervals subjects will be asked:

“Since you were last asked, have you felt unwell or different from usual?”

Out of range laboratory results arising once study treatment has begun, will be reviewed by the Investigator. The Investigator will determine whether the signs and symptoms represent clinically significant changes from the subject's baseline, and if so, they should be recorded as an AE.

The Investigator will evaluate all AEs as to:

- Seriousness: See definition in Appendix 3
- Severity: See definition in Appendix 3.
- Causal Relationship to study drug: See definition in Appendix 3.
- Outcome.

All AEs, serious and non-serious, must be recorded in the AE section of the CRF. SAEs must also be reported to the Sponsor in 24 hours through the SAE form.

After the end of study period, including follow-ups, only if a SAE is believed to be related to the study drug administration should it be reported to the Sponsor.

Adverse Events causing treatment discontinuation

If a subject is withdrawn from the study as a consequence of an AE, this must be recorded and reasoned in the CRF, and the subject must be followed up until the AE outcome resolution.

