3.5.2 Secondary efficacy endpoints

The secondary efficacy endpoints are the following:

- number of moderate/severe COPD exacerbations;
- number of re-hospitalizations and deaths (all cause);
- QoL variation measured as change in CAT total score from baseline to end of treatment period;
- change in mMRC dyspnea score from baseline to end of treatment period;
- number of pneumonia events;
- number of acute cardiac events;
- number of cardiovascular deaths;
- change in FEV1 from baseline to the end of treatment period;
- change in FVC from baseline to the end of treatment period.

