7.2 Analysis of secondary efficacy endpoints

Definitions and data conventions

Number of re-hospitalizations and death

The number of re-hospitalizations and deaths will be calculated per-subject as the sum of the number of hospitalizations as recorded in the ‘COPD Exacerbation Form’ and the deaths (all cause).

Number of moderate/severe COPD exacerbations

The number of moderate/severe COPD exacerbations will be calculated per-subject as the sum of the number of COPD exacerbations recorded as “Moderate” or “Severe” in the ‘COPD Exacerbation Form’.

Number of pneumonia events

The number of pneumonia events will be calculated per-subject as the sum of adverse events classified with the following System Organ Classes/Preferred Terms:

System Organ Class	Preferred Term
Respiratory, thoracic and mediastinal disorders	
 • Pneumonia NOS • Acute pneumonia • Lung infection • Multilobar pneumonia • Bronchopneumonia • Pneumonia lobar • Pneumonia, organism unspecified • Bronchopneumonia NOS • Acute bronchopneumonia • Community acquired pneumonia • Lobar pneumonia NOS • Ventilator associated pneumonia • Healthcare associated pneumonia • Pneumonia recurrent • Bronchopulmonary infection

Forms			
Title	Statistical Analysis Plan Template		
Code	Version	Effective Date	Page
FRM_ST03_032	02	02 Oct 2017	20 of 26

	
 Pulmonary suppuration Lung infection NOS Pleuropneumonia Bronchopneumonia, organism unspecified Bilateral bronchopneumonia Infectious pneumonitis Nosocomial pneumonia Bronchial pneumonia Bilateral pneumonia Hospital acquired pneumonia Right middle lobe pneumonia Lobar pneumonia
--	---

Number of acute cardiac events

The number of acute cardiac events will be calculated per-subject as the sum of adverse events classified with the following System Organ Classes/Preferred Terms:

System Organ Class	Preferred Term
Cardiac disorders	
 Heart failures -Coronary artery disorders Cardiac arrhythmias Embolic stroke Haemorrhagic stroke Thrombotic stroke

Time on study

Time on study (years) will be calculated using the following formula:

Time on study (years) = (Date of patient completion or withdrawal - Date of randomization +1)/365.25.

Log-time on study (years)

The log-time on study in years will be calculated using the following formula:

$$\text{Log-time on study} = \ln(\text{time on study})$$

Statistical analysis

Analysis will be performed on the ITT population.

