Number of re-hospitalizations and deaths

The number of re-hospitalizations and deaths of all cause (1, 2, 3, 4, >4) will be summarised by using frequency distributions and percentages.

Comparison between treatments will be performed using a Poisson regression model. The model will include the number of events as dependent variable, treatment group and center as qualitative independent variables and age as quantitative independent variable. Log-time on study (in years)

Forms			
Title	Statistical Analysis Plan Template		
Code	Version	Effective Date	Page
FRM_ST03_032	02	02 Oct 2017	21 of 26

will be used as an offset. The overdispersion parameter based on the deviance will be considered in order to account for between-patient variability in the event rate and standard errors will be estimated allowing for extra-Poisson variation.

The number of patients and the number of patients considered in the model will be provided by treatment. P-values of the independent variables based on Wald chi-square test will also be presented.

The adjusted mean rates per patient per year in each treatment group and their 95% CIs will be presented, and the adjusted rate ratio between treatments will be provided with the associated 95% Wald CI and p-value.

The following SAS® code will be used to estimate the Poisson regression model:

```
proc genmod data = dataset;
class TMT CENTER;
model VAR = TMT CENTER AGE / offset=log_time dist=poisson link=log dscale wald type3;
lsmeans TMT / exp cl;
lsestimate 'LABD vs LABD + ICS' TMT 1 -1 / exp cl;
run;quit;
```

where VAR represents the number of re-hospitalizations and deaths, TMT the treatment group, CENTER the center, AGE the age and log_time the logarithm of the time on study in years.

The variable tmt will be ordered in SAS in the following order:

- 1 = LABD;
- 2 = LABD + ICS.

Number of moderate/severe COPD exacerbations

The same analyses described for the number of re-hospitalizations and deaths will be performed for the number of moderate/severe COPD exacerbations (1, 2, 3, 4, >4).

Number of pneumonia events

The same analyses described for the number of re-hospitalizations and deaths will be performed for the number of pneumonia events (1, 2, 3, 4, >4).

Number of acute cardiac events

The same analyses described for the number of re-hospitalizations and deaths will be performed for the number of acute cardiac events (1, 2, 3, 4, >4).

Number of deaths

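### The SAP counts acute cardiac events from an adverse-event list that does not match the visit-based definition in protocol 8.1.4, and SAP 4.8 does not declare the difference

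*SAP*

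**What the plan says.** Protocol 8.1.4, headed as acute cardiac events, makes two statements. The first concerns recording: "Acute cardiac events will be recorded based on the clinical evaluation". The second is the definition: "Acute CV events are defined as an inpatient or emergency department visit with a primary diagnosis of any of the following conditions". Four diagnosis groups follow, with ICD-9-CM codes: coronary heart disease (410-414), cardiac arrhythmia (427), heart failure (428), and a stroke group worded "or ischemic stroke (ICD-9-CM codes 433-434".

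SAP 3.5.2 lists the "number of acute cardiac events" among the secondary efficacy endpoints. SAP 7.2 derives it as follows: "The number of acute cardiac events will be calculated per-subject as the sum of adverse events classified with the following" classes and terms. The table has one system organ class, cardiac disorders, and six entries. The first two are heart failures and coronary artery disorders; the other four are "Cardiac arrhythmias Embolic stroke Haemorrhagic stroke Thrombotic stroke".

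The count then goes into a model: "The same analyses described for the number of re-hospitalizations and deaths will be performed for the number of acute cardiac events". That means the Poisson regression with treatment, centre and age, reporting an adjusted rate ratio with a 95% confidence interval and p-value.

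SAP 4.8 lists two changes from the protocol: paired t-test p-values are dropped, and vital signs and physical examination data are only listed.

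**The concern.** The two documents count different things under one endpoint name. The protocol counts hospital or emergency visits with a specified main diagnosis. The SAP counts adverse events with a listed code, wherever they were managed and whatever the main diagnosis of any visit was.

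The visit condition is the part of the protocol's definition that makes an event acute, and the SAP puts nothing in its place. A visit with a main diagnosis also leaves less to site reporting than an adverse-event entry does, which is relevant in an open-label trial.

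At stake is what the reported rate ratio means. Under the SAP rule it could include events that the protocol's definition leaves out, and SAP 4.8 would not alert a reader to this.

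**Working it through.** The plan gives no expected rate for acute cardiac events, so there is no figure to reproduce. The check sets the two definitions side by side.

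| Element | Protocol 8.1.4 | SAP 7.2 |
|---|---|---|
| Care setting | Hospital stay or emergency visit | None stated |
| Main diagnosis of the visit | Must be a listed condition | None stated |
| Coronary disease | 410-414 | Coronary artery disorders |
| Arrhythmia | 427 | Cardiac arrhythmias |
| Heart failure | 428 | Heart failures |
| Ischaemic stroke | 433-434 | Embolic and thrombotic entries only |
| Haemorrhagic stroke | Not listed | Listed |

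**Counts from the table**
- Protocol conditions carried into the SAP: 0 of 2.
- SAP entries outside the protocol's four groups: 1 of 6 (haemorrhagic stroke).
- Changes declared in SAP 4.8 that cover this: 0 of 2.

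**Can events without a visit enter the count?** Protocol 8.3.4 says "All AEs, serious and non-serious, must be recorded in the AE section of the CRF". The adverse-event definition in Protocol Appendix 3 covers worsening of existing disease as well as new disease. SAP 7.2 applies no filter for seriousness or visit. An arrhythmia or a worsening of heart failure managed entirely outside hospital would therefore count if it were recorded and coded to a listed entry.

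**Is that plausible here?** Inclusion criterion 6 requires heart failure, ischaemic heart disease or atrial fibrillation. Each corresponds to an SAP entry (3 of 3). This shows only that the labels overlap. Under SAP 5.5, disease ongoing at screening is a concomitant disease, so a chronic condition is not itself a counted event. It would have to worsen or recur and be reported as an adverse event.

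**What depends on coding?** All six entries stand under the cardiac disorders class, and the SAP does not say whether that column filters the events. Three entries read as group labels although their column is headed as preferred terms. Whether a given stroke would be counted depends on both points, and the coding dictionary is not part of the documents.

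**How large is the effect?** The documents give no acute cardiac event rate, no share of such events managed outside hospital and emergency care, and no haemorrhagic stroke rate. The number of events added or missed, and any shift in the rate ratio, cannot be calculated.

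**The case against.** **The protocol is itself loose.** The endpoint is named acute cardiac events, but the definition is attached to acute CV events, and the recording sentence refers to clinical evaluation. This stands as a criticism of 8.1.4, and it means the wording has to be settled first. It does not remove the mismatch. The visit-based definition is the only one under that heading, and the recording sentence does not say what qualifies as an event. Using adverse-event records as the source is not the problem; the two missing conditions and the added stroke type are.

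**The SAP may follow another protocol text.** Its revision history says the draft was based on protocol version 1.0 of 12.03.2018. The spirometry footnote in SAP 3.2 gives 8 weeks after discharge, where the supplied protocol's schedule gives 4 weeks since the last exacerbation. A reader might infer that the SAP authors knowingly altered the endpoint without saying so. The documents do not support that, because section 8.1.4 of version 1.0 cannot be checked here.

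**The stroke entries may have little effect.** If the class column is a filter, stroke events may be counted differently from what the list suggests. A reader might also infer that ischaemic strokes coded as neither embolic nor thrombotic will be lost. That is a coding check to make, not a demonstrated defect.

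**The consequence is limited.** This is one of nine secondary endpoints, and the adverse-event tables in SAP 8.1 would still show the individual terms. That is correct, but those tables do not give the adjusted rate ratio for the protocol's endpoint.

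**Conclusion.** The concern holds as a mismatch between the SAP and the supplied protocol on the definition of a modelled secondary endpoint. Neither of the protocol's two conditions is carried over, one of six entries falls outside its diagnosis groups, and SAP 4.8 is silent. If the SAP rule is followed as written, the rate ratio will not be for the endpoint that protocol 8.1.4 defines.

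This rests on reading the visit-based sentence in 8.1.4 as the endpoint definition, and on the supplied protocol being the one that governs the analysis.

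It would go too far to say that the treatment comparison is biased. The documents do not allow the size or direction of any effect to be derived. The primary endpoint, its analysis and the sample size (464 per group, 516 with dropout) are not affected. The point should be corrected, but it does not threaten the main result.

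**What to change.** Before outcomes are reviewed by arm:

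1. Reconcile the acute cardiac and acute CV wording in protocol 8.1.4 and confirm which definition is the endpoint. The remaining steps assume that the visit-based one is confirmed.
2. Align the SAP 7.2 table with it. Remove haemorrhagic stroke, make the stroke entry cover ischaemic stroke generally, state whether the system organ class column is a filter, and state the coding level at which each entry applies. Check the entries against MedDRA 21.0, the version named in SAP 8.1.
3. Restrict the count to hospital or emergency events with a listed main diagnosis wherever the collected data identify them. The hospitalization criterion for seriousness in Protocol Appendix 3 should not be the only filter if it drops qualifying visits: it describes detention at the hospital or emergency ward, so emergency visits without detention could be missed.
4. Declare in SAP 4.8 any part of the definition that cannot be applied. If the broader adverse-event count is kept instead, declare and justify it there.

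The work is a clarification of 8.1.4, a table edit, an entry in SAP 4.8 and a coding check. The CRF is not among the documents, so it is unknown whether emergency visits without detention, or the main diagnosis of each visit, can be identified. Restricting the count will probably leave fewer events and a somewhat less precise rate ratio.

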4.4. End of Study Definition

A participant is considered to have completed the study if he/she has completed all phases of the study including the last visit (Visit 7).

The end of the study is defined as the date of the last visit of the last participant in the study.

5. Study Population

Prospective approval of protocol deviations to recruitment and enrollment criteria, also known as protocol waivers or exemptions, is not permitted.

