Participants will be asked to complete the CAT and mMRC questionnaires.

Medical history and history of COPD and CV disease will be reviewed and updated as necessary.

Participants will be asked about treatment. Information about any hospitalizations or any unexpected medical events, particularly moderate exacerbations treated with antibiotics and/or steroids will be collected. Information will be obtained by reviewing the patient's medical records and prescribed medication and also from direct questioning of the participant.

The participant's ongoing treatments (concomitant medications) will be reviewed and updated as necessary both for COPD and CV comorbidities, particularly HF, IHD and/or AF. Details of all concomitant medications will be recorded.

Participants will be questioned about the occurrence of any serious adverse events and details will be recorded on the eCRF.

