8.3.1. Time Period and Frequency for Collecting AE and SAE Information

All AEs (serious and non-serious) will be collected and registered by the investigator in the CRF, from the start of study treatment until the last follow up visit at the time points specified in the SoA (Section 1.3). SAEs will be collected starting from Informed Consent signature (see 8.3.2).

Investigators are not obligated to actively seek AEs after conclusion of the study participation. However, if the investigator learns of any SAE, including a death, at any time after a participant has been discharged from the study, and he/she considers the event to be reasonably related to the study intervention or study participation, the investigator must promptly notify the sponsor.

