5.3 Study discontinuations

Definitions and data conventions

Date of completion/discontinuation

Date of study completion will be the date of study end recorded in the study conclusion/withdrawal form.

If the date of study completion is missing, the date of last study visit performed (i.e. Date of Visit 6) will be used.

Forms			
Title	Statistical Analysis Plan Template		
Code	Version	Effective Date	Page
FRM_ST03_032	02	02 Oct 2017	14 of 26

Date of discontinuation will be the date of withdrawal recorded in the study conclusion/withdrawal form.

Statistical analysis

Randomised patients who completed the study will be presented by treatment and overall for the Randomised population. Randomised patients who discontinued from the study prematurely will also be presented with a breakdown of the reasons for discontinuation by treatment and overall for the Randomised population.

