8.1 Adverse events

Definitions and data conventions

Pre-treatment adverse events

An AE will be classified as pre-treatment AE if it starts before the date of randomization (AE onset date < date of randomization).

Treatment-emergent adverse event (TEAE)

An AE will be classified as a TEAE if it starts on or after the date of randomization (AE onset date \geq date of randomization).

In case of missing or incomplete dates not allowing a direct allocation to any of the two categories of AEs, a worst-case allocation will be done according to the available parts of the onset and the end dates. The AE will be allocated to the first category allowed by the available data, according to the following order:

- TEAE
- Pre-treatment.

Serious adverse event (SAE)

A SAE is an AE judged as serious.

Adverse drug reaction (ADR)

An ADR is an AE with relationship to study treatment equal to “Yes”.

Severe adverse event (SAE)

A SAE is an AE judged as severe intensity.

Adverse event leading to study withdrawal

An AE leading to study withdrawal is an AE with action taken equal to “Drug withdrawn” or “Drug interrupted”.

Count of adverse events

Two AEs with the same Preferred Term (PT) and classified in the same category (pre-treatment AE or TEAE) will be considered as two different events when calculating the “number of events” in the tables.

Statistical analysis

Pre-treatment AEs and TEAEs will be presented separately. Pre-treatment AEs will be presented in the listings only.

The number of treatment-emergent AEs, SAEs, ADRs, severe AEs and AEs leading to discontinuation, and the number and the percentage of patients experiencing treatment-emergent AEs, SAEs, ADRs, severe AEs and AEs leading to discontinuation will be summarised by treatment group. Differences between groups will be evaluated using Chi-square test or Fisher’s exact test (if more than 20% of the cells in a contingency table have expected counts less than 5).

Title	Statistical Analysis Plan Template		
-------	------------------------------------	--	--

Code	Version	Effective Date	Page
FRM_ST03_032	02	02 Oct 2017	24 of 26

AEs will be coded using the MedDRA dictionary (version 21.0). The SOCs and PTs will be used for tabulation. The number of treatment-emergent AEs and the number and the percentage of patients with at least one treatment-emergent AE will also be presented by SOC and PT by treatment group.

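### The SAP count endpoints have no end date, and their person-time ends at a completion date that may mean Visit 6 or Visit 7, so events and exposure are not assured to match

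*SAP*

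**What the plan says.** **Counts.** SAP 7.2 defines the pneumonia and acute cardiac counts as per-subject sums of coded adverse events. Hospitalisations and moderate or severe exacerbations are summed from the COPD Exacerbation Form, with all-cause deaths added to the hospitalisations. None of these definitions has an end date.

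**Person-time.** All the Poisson models use the log of one exposure variable as offset: "Time on study (years) = (Date of patient completion or withdrawal - Date of randomization +1)/365.25". SAP 5.3 defines the completion date: "Date of study completion will be the date of study end recorded in the study conclusion/withdrawal form". It adds: "If the date of study completion is missing, the date of last study visit performed (i.e. Date of Visit 6) will be used". Protocol 4.4 regards a participant as a completer only "if he/she has completed all phases of the study including the last visit (Visit 7"). Yet protocol section 8 labels Visit 6 as the end of study and Visit 7 as a follow-up after it, and SAP 7.1 also treats Visit 6 as the end-of-study visit.

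**Collection.** The schedules in protocol 1.3 and SAP 3.2 mark adverse event review at Visits 2 to 6 and serious adverse event review at Visits 2 to 7. The adverse event question in the Visit 7 text of protocol section 8 is limited in the same way: "Participants will be questioned about the occurrence of any serious adverse events and details will be recorded on the eCRF". Protocol 8.3.1, however, says that serious and non-serious events are collected "from the start of study treatment until the last follow up visit at the time points specified in the SoA", and 8.3.2 also extends collection into the follow-up period. Section 8.3.1 therefore names an end point that the schedule it defers to does not support for non-serious events.

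**The concern.** A rate per patient-year is meaningful only if events and exposure cover the same calendar window. Here neither end is fixed, and the two ends can differ. Two programmers following the SAP could derive person-time three months apart for every completer. Within one derivation, patients whose completion date is missing would be treated differently from the rest.

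Pneumonia is the endpoint most at risk, because part of it is non-serious. It is also a stated harm objective: SAP 2.2 asks whether a year of combination treatment raises pneumonia risk. SAP 7.2 will report adjusted mean rates per patient per year for each arm, so a window error goes straight into the published figures. The primary endpoint is censored at Visit 6 or withdrawal, and the CAT, mMRC, FEV1 and FVC changes stop at the end of treatment. Only the count endpoints can drift into months 13 to 15.

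**Working it through.** **1. The plan's own figures.** The documents give no figure for person-time or for pneumonia or cardiac rates. The only planning figure is 464 per group, 516 after dropout. It reproduces: HR = ln(0.91)/ln(0.85) = 0.580. Freedman's formula gives (1.960 + 0.842)² × [(1 + 0.580)/(1 − 0.580)]² / (2 × 0.12) = 463.7, so 464; and 464/0.90 = 515.6, so 516. It rests on the primary endpoint alone and is untouched by this point.

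**2. Inputs.** Treatment lasts 12 months and follow-up 3 months (protocol synopsis). Let s be the share of pneumonias that are serious. The documents do not give s, so the full range 0 to 1 is shown. The event rate is taken as constant and the patient as a completer.

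**3. Completion at Visit 7, schedule followed.** All events are captured for 12 months, only serious ones for the next 3, and exposure is 15 months. Reported/true rate = (12 + 3s)/15.

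**4. Completion at Visit 6, schedule followed, counts not cut.** Same events, exposure 12 months. Reported/true rate = (12 + 3s)/12.

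| s | Completion at Visit 7 | Completion at Visit 6 |
|---|---|---|
| 0 | 0.80 | 1.00 |
| 0.25 | 0.85 | 1.06 |
| 0.50 | 0.90 | 1.13 |
| 0.75 | 0.95 | 1.19 |
| 1 | 1.00 | 1.25 |

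**5. Completion at Visit 7, all adverse events collected to Visit 7** (protocol 8.3.1 and 8.3.2). Reported/true rate = 15/15 = 1.00. No mismatch.

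**6. Hospitalisations and exacerbations.** These do not depend on adverse event review, and the schedule and Visit 7 text have them collected at Visit 7. With completion at Visit 7 the factor is 15/15 = 1.00. With completion at Visit 6 and uncut counts it is 15/12 = 1.25.

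**7. One patient under the SAP 5.3 fallback.** Exposure falls from about 15/12 = 1.25 years to 1.00 year.

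**8. Rate ratio (LABD+ICS over LABD), effect lost after month 12.** With no withdrawal the denominators cancel. If the true ratio R applies on treatment and 1.0 afterwards, the reported ratio is (R + 0.25s)/(1 + 0.25s). With R = 1.5 this is 1.47 at s = 0.25, 1.44 at s = 0.5 and 1.40 at s = 1. Now assume 10% withdrawal in each arm, at 6 months on average and with no follow-up visit. Mean time on treatment is 0.9 × 12 + 0.1 × 6 = 11.4 months and mean follow-up is 0.9 × 3 = 2.7 months. At s = 0.25 the ratio is (1.5 × 11.4 + 0.25 × 2.7)/(11.4 + 0.25 × 2.7) = 1.47; at s = 0.75 it is 1.43 (1.425 before rounding).

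**9. Rate ratio, unequal withdrawal and no true effect.** Under the same withdrawal assumptions and s from 0.25 to 0.75, the ratio is 0.991 to 1.008 for 5% (LABD) against 15% (LABD+ICS), and 0.976 to 1.022 for 5% against 30%. With equal withdrawal and a constant effect it does not change.

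**The case against.** The strongest reply is that a coherent whole-study reading exists. Protocol 4.4 puts completion at Visit 7, 8.3.1 and 8.3.2 collect all adverse events through follow-up, and the count endpoints, unlike the CAT, mMRC and spirometry changes, are not limited to the end of treatment. On that reading step 5 applies and nothing is wrong. The Visit 6 fallback matters only when a completion date is missing. This stands as far as it goes. A reader might infer that the annual rates are wrong whichever visit completion means, or that non-serious events certainly go uncollected after Visit 6; the documents support neither. They conflict, because 8.3.1 itself defers to a schedule that stops general review at Visit 6.

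Nor does Visit 7 ask about serious events alone. The text also seeks hospitalisations and other unexpected medical events, including those treated with antibiotics. A non-serious pneumonia might surface there, but nothing says it would be entered as an adverse event, which is what the SAP counts.

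A reader might also infer that the pneumonia ratio is necessarily pulled towards 1 and a harm hidden. Protocol 6.7 says patients continue their treatment after the randomised period, while the Visit 6 text leaves it to the investigator's discretion. Dilution is therefore conditional, and modest in step 8 even if the effect vanishes completely. The planning ratio of 9% to 15% should not be put through that formula, since it compares first-event proportions and not recurrent-event rates.

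Two further limits hold. Acute cardiac events are defined in protocol 8.1.4 as inpatient or emergency visits, so most would be serious and captured to Visit 7. The treatment-emergent rule in SAP 8.1 ("An AE will be classified as a TEAE if it starts on or after the date of randomization") also lacks an end date, but its tables use counts and percentages without person-time, so the rate error does not arise there.

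**Conclusion.** The point holds as a conflict between documents that leaves alignment unassured; it does not establish a definite bias. If sites follow the schedule, the pneumonia rate per patient-year for a completer lies between 0.80 and 1.00 of its true value with completion at Visit 7, and between 1.00 and 1.25 with completion at Visit 6 and uncut counts. Hospitalisation and exacerbation rates are up to 25% too high with completion at Visit 6. If all adverse events are collected to Visit 7 and completion is Visit 7, there is no error.

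The between-arm ratio is far less sensitive. It moves appreciably only if withdrawal differs strongly between arms or the effect changes after month 12; a ratio of 1.5 becomes about 1.40 to 1.47 if the effect vanishes. The serious share, withdrawal pattern, constant rate and loss of effect are all assumptions. The primary analysis and the sample size are not affected. This should be corrected before analysis, but it does not threaten the trial's main conclusion.

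**What to change.** - In SAP 7.2, count only events with onset from randomisation to Visit 6, or to withdrawal if earlier. Set the offset to (date of Visit 6 or withdrawal − date of randomisation + 1)/365.25. This matches the one-year pneumonia objective and the censoring of the primary endpoint.
- Report events between Visit 6 and Visit 7 in a separate table or listing.
- Give completion one meaning across SAP 5.3 and protocol 4.4.
- Reconcile protocol 8.3.1 and 8.3.2 with the schedule and the Visit 7 text.

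The cost is some wording and one derived date; no new data are needed. The downside is that follow-up events leave the main count models, so a completer contributes 12 months instead of 15 (20% less observation), although those events stay reported. A common window to Visit 7 would also align events and exposure. It would work only if all adverse events were in fact recorded to Visit 7, and it would move the pneumonia analysis away from the treatment year.
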